11.2 Patient Randomization

Subjects will be randomized into DUR-928 10 mg and 50 mg treatment groups at a 1:1 ratio, without stratification.

11.3 Definition of Analysis Populations

Intent-to-Treat (ITT) Population: The ITT population will include all randomized subjects independent of their exposure to test drug.

Safety Population: The Safety population will include all subjects who received any amount of test drug. The Safety population will be used for all safety analyses.

Modified Intent-to-Treat (mITT) Population: The mITT population will include all randomized subjects who receive any test drug.

All efficacy endpoints will be analyzed using the mITT population. The disposition data will be summarized using ITT population.

11.4 General Statistical Analysis Considerations

Study data will be summarized by treatment group and overall using descriptive statistics. Categorical variables will be reported with frequencies and percentages. Continuous variables will be reported with number of subjects, mean, standard deviation (SD), median, minimum, and maximum. 95% confidence intervals will also be provided when appropriate. All summaries, statistical analyses, and individual patient data listings will be completed using Version 9.3 or later of the SAS Statistical Analysis System (SAS Institute, Inc. Cary, NC).

The primary efficacy endpoint of detecting a signal with regards to the decrease of the percentage change from baseline in ALP will be tested in the ‘pooled group’ of both dose levels. The comparison between the dose levels will be performed by exploratory testing. Secondary and other endpoints will be analyzed and explored in a descriptive manner.

11.5 Methodology for Dropouts and/or Missing Data

Missing data will not be imputed except missing date of concomitant medication. Missing dates of concomitant medication may be imputed according to rules to be specified in the SAP. Subjects who discontinued the study early will be summarized by reasons and treatment group.

11.6 Demographic and Baseline Characteristics

Demographic and baseline characteristics will be summarized using descriptive statistics specified in section 11.5. Baseline is defined as the last non-missing value before the first dose of study drug.

11.7 Statistical Analyses of Efficacy Endpoints

11.7.1 Primary Efficacy Endpoint

- % change from baseline of serum ALP to the end of the study treatment
- % change from baseline of serum ALP at all post-baseline visits and throughout the follow-up period

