2.0 TRIAL SYNOPSIS

Title of Trial: A Randomized, Open-label, Phase 2 Study to Evaluate Safety and Efficacy of DUR-928 in Subjects with Primary Sclerosing Cholangitis (PSC)

Sponsor: DURECT Corporation

Phase of Development: Phase 2

Objective: Primary:

- To evaluate safety of DUR-928 in subjects with PSC
- To evaluate percent change (%) of serum alkaline phosphatase (ALP) from baseline

Secondary:

To evaluate % change of liver enzymes and selected biomarkers from baseline

Efficacy Endpoints: Primary Efficacy Endpoint

% change of serum ALP from baseline through the end of the study treatment and throughout the follow-up period.

Secondary Efficacy Endpoint:

- % of subjects with $\geq 20\%$ reduction of serum ALP from baseline
- % of subjects with $\geq 30\%$ reduction of serum ALP from baseline
- % of subjects with $\geq 40\%$ reduction of serum ALP from baseline
- % change of liver enzymes, including ALT, AST, GGT, bilirubin from baseline, through the end of study treatment and throughout the follow-up period.
- % change of selected biomarkers from baseline through the end of study treatment and throughout the follow-up period.
- % change of serum bile acids (sBA) from baseline through the end of study treatment and throughout the follow-up period.

PPD/CCI

A large rectangular area of the page is completely blacked out, indicating redacted information. The text "PPD/CCI" is visible at the top left corner of this redacted area.

Safety Assessments:

- Adverse Events (AEs) will be recorded from signing the informed consent form through the end of study or early termination visit
- Vital Signs, Physical Examinations and 12-lead ECG findings
- Safety Laboratory Tests (chemistry, hematology, and urinalysis)

[figure not shown]
Trial Design: The proposed study is a randomized, open-label, 2 dose (10 mg and 50 mg, both once daily) study to evaluate the safety and efficacy of DUR-928 administered orally for 28 days, both at the end of dosing and throughout the follow-up period (28 days post-dose).

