11.0 STATISTICAL METHODS AND DATA ANALYSIS

11.1 Sample Size Determination

A sample size estimation was performed for the primary efficacy endpoint 'Percentage change from baseline to week 4 in the serum alkaline phosphatase (ALP) level.

Forty subjects will be randomized in total. Considering an early withdrawal rate of 10%, a sample size of 36 subjects (18 subjects per dose group) provides a statistical power of 80% to detect a 15% decrease (with a standard deviation of 35%) compared to baseline in serum ALP after 4 weeks of treatment using a one-group t-test. ^{PPD/CCI} [REDACTED]

[REDACTED]

Details of statistical measures and data analysis will be further specified in the Statistical Analysis Plan for this study.

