11.7.4 Adjustment for Multiple Hypotheses Testing

Only the primary efficacy criterion will be tested confirmatorily, thus no adjustment for multiple testing is required.

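### The primary ALP endpoint is a single week-4 change in 11.1 but also takes in every other post-baseline visit in 11.7.1; the no-adjustment statement in 11.7.4 is justified only for a single test such as 11.1's

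*Combined protocol and SAP*

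**What the plan says.** **One time point.** Section 11.1 bases the sample size on "the primary efficacy endpoint 'Percentage change from baseline to week 4 in the serum alkaline phosphatase (ALP) level". It claims 80% power with 36 evaluable subjects for a 15% fall (SD 35%) in a one-group t-test after 4 weeks. The power paragraph of the synopsis also refers to ALP after 4 weeks and the one-group t-test. The first bullet of 11.7.1, change to the end of study treatment, is consistent with this, because dosing lasts 28 days.

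**A span or many time points.** The synopsis gives the primary endpoint as percent "change of serum ALP from baseline through the end of the study treatment and throughout the follow-up period", and 8.1 is worded almost identically. Neither names a visit. The second bullet of 11.7.1, also under the primary heading, is percent "change from baseline of serum ALP at all post-baseline visits and throughout the follow-up period".

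**What is tested.** Section 11.4 says: "The primary efficacy endpoint of detecting a signal with regards to the decrease of the percentage change from baseline in ALP will be tested". Both doses are pooled for this test, and no visit is named. The section then says: "Secondary and other endpoints will be analyzed and explored in a descriptive manner". Section 11.7.4 says: "Only the primary efficacy criterion will be tested confirmatorily, thus no adjustment for multiple testing is required".

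**The concern.** The plan gives two answers to the question of which ALP result decides the trial. Under 11.1 it is one number, at week 4. Under 11.7.1 it is that number together with the results at all other post-baseline visits, and nothing ranks the second bullet below the first. The sentence in 11.4 that makes endpoints descriptive covers secondary and other endpoints only, so it does not reach visits listed as primary.

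Section 11.7.4 rests on there being a single confirmatory criterion. That is true of 11.1, but 11.7.1 does not supply a single criterion. The trial is open-label, and the protocol itself calls the primary test confirmatory. If week 4 were negative and, say, Day 15 or Day 42 were positive, a reader of the visible text could not tell whether the trial had met its primary endpoint.

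**Working it through.** **1. Reproduce the plan's power.** Inputs from 11.1: fall 15%, SD 35%, n = 36 evaluable, one-group t-test. Section 11.4 supplies the pooling of doses. Alpha and sidedness are not visible (the text after the test is blacked out), so both are varied.

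Noncentrality = (15/35) × √36 = 2.571, with 35 degrees of freedom. Power is the probability that a noncentral t exceeds the critical value.

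| Test | Critical t | Power |
|---|---|---|
| n = 36, one-sided 5% | 1.690 | 81.0% |
| n = 36, two-sided 5% | 2.030 | 70.6% |
| n = 18 (one dose), one-sided 5% | 1.740 | 54.0% |

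The stated 80% reproduces for one pooled test at one-sided 5%, and 36 is the smallest n that reaches it. Dropout also agrees: 36/0.9 = 40. The sample size therefore belongs to a single test at a single time point.

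**2. Count the ALP time points in the second 11.7.1 bullet.** ALP is in the chemistry panel (9.5.1). Chemistry is drawn on Days 8, 15, 22 and 28 (7.3.3), Day 42 (7.3.4) and Day 56 (7.3.5). That makes six post-baseline visits, of which Day 28 is the week-4 visit.

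**3. Error rate under different readings, with no drug effect.** Model: 36 subjects, six visits, equal correlation ρ between the percent changes at any two visits (an assumption; the documents give none). At each visit j, t_j = mean_j / (SD_j/√36), and a fall is declared if t_j < −1.690 (one-sided) or |t_j| > 2.030 (two-sided). The any-visit error is the chance that at least one of the six crosses. With independent visits it would be 1 − 0.95⁶ = 26.5%. For correlated visits it was simulated with 200,000 trials per value of ρ:

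| ρ | Any of six, one-sided | Any of six, two-sided |
|---|---|---|
| 0.5 | 19% | 21% |
| 0.7 | 15% | 17% |
| 0.8 | 13% | 14% |
| 0.9 | 10% | 11% |
| 0.95 | 8% | 9% |

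The single week-4 test, simulated in the same way, gives 5%. Requiring success at all six visits gives 0.1% (ρ = 0.5) to 2.5% (ρ = 0.95) one-sided, so that rule would need no adjustment either.

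**4. Set the sections side by side.** Section 11.7.4 is correct if the confirmatory test is the one in 11.1. It is also correct for any other single pre-specified visit, a fixed sequence, an all-visits rule or one summary test. It is incorrect only if success at any of several listed visits counts. The visible text does not say which of these applies to the endpoint as 11.7.1 lists it.

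**The case against.** The best defence is that the sections, read together, already give one test. Sections 11.4 and 11.7.4 speak of the primary endpoint and criterion in the singular. Section 11.1 describes one t-test at one time point, and the first bullet of 11.7.1 and the synopsis power paragraph agree with it. Section 11.7.2 uses the same pair of phrases (end of treatment, then all post-baseline visits) for the ALP responder rates, bilirubin, ALT, AST and GGT, which suggests that the second bullet of 11.7.1 is a reporting schedule. The text after the t-test in 11.1 is blacked out, and 11.1 leaves further detail to a Statistical Analysis Plan whose text is not in the document reviewed. The trial is also a 40-subject Phase 2 study looking for a signal.

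Much of this stands. It makes 11.1 the likely intent and keeps the severity down. It does not remove the conflict: the second bullet sits under the primary heading, no visible sentence calls it descriptive, and text elsewhere would not change what the visible sections say.

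A reader might infer three stronger things that the documents do not support.

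- **That the trial's type I error is inflated.** No section contains an any-visit success rule, and the test actually sized has a 5% error at the assumed level.
- **That the trial is underpowered because alpha must be split over six visits.** The plan proposes no such split.
- **That the synopsis and 8.1 list every visit as primary.** They give a time span; only 11.7.1 refers to all post-baseline visits.

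The missing alpha and sidedness lie beside a redaction and are not counted as a fault. How early stoppers enter the end-of-treatment value is a separate question that this point does not depend on.

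**Conclusion.** Wrong as written: an internal contradiction over the primary endpoint, of minor to moderate severity. The contradiction between 11.1 and the second bullet of 11.7.1 is in the visible text and needs no assumption. The span wording in the synopsis and 8.1 does not resolve it, and neither does 11.4.

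The numerical consequence is conditional. It is nil under 11.1. It is about 8% to 19% instead of 5% if success at any of the six visits counted, assuming a one-sided 5% level, n = 36 and an equal between-visit correlation of 0.95 to 0.5. The one-sided 5% level is inferred only because it reproduces the stated power.

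**What to change.** State in the synopsis, 8.1, 11.4 and 11.7.1 that the only confirmatory test is the pooled-dose percent change in ALP from baseline to week 4 (Day 28 visit), as 11.1 has it. Move the second bullet of 11.7.1, covering the other visits and follow-up, to secondary endpoints reported descriptively.

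The cost is wording in four sections. Visits, data, number of subjects and the sized test do not change, and 11.7.4 then holds without amendment. The trade-off is that ALP after dosing becomes descriptive, although the synopsis sets out to evaluate the drug "both at the end of dosing and throughout the follow-up period (28 days post-dose"). If the sponsor wants a confirmatory claim in follow-up, a fixed sequence with week 4 first would also need no alpha adjustment, but it would have to be written down in advance.

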11.7.2 Secondary Efficacy Endpoints

The secondary efficacy endpoints are:

- % of subjects with $\geq 20\%$ reduction of serum ALP from baseline to the end of the study treatment
- % of subjects with $\geq 30\%$ reduction of serum ALP from baseline to the end of the study treatment
- % of subjects with $\geq 40\%$ reduction of serum ALP from baseline to the end of the study treatment
- Mean and % change from baseline of bilirubin (total and direct) to the end of the study treatment
- % change from baseline of ALT to the end of the study treatment
- % change from baseline of AST to the end of the study treatment
- % change from baseline of GGT to the end of the study treatment
- % of subjects with $\geq 20\%$ reduction of serum ALP from baseline at all post-baseline visits and throughout the follow-up period
- % of subjects with $\geq 30\%$ reduction of serum ALP from baseline at all post-baseline visits and throughout the follow-up period
- % of subjects with $\geq 40\%$ reduction of serum ALP from baseline at all post-baseline visits and throughout the follow-up period
- % change from baseline of bilirubin (total and direct) at all post-baseline visits and throughout the follow-up period
- % change from baseline of ALT at all post-baseline visits and throughout the follow-up period

- % change from baseline of AST at all post-baseline visits and throughout the follow-up period
- % change from baseline of GGT at all post-baseline visits and throughout the follow-up period
- % change of selected biomarkers (to be specified in the Statistical Analysis Plan (SAP) from baseline and throughout the follow-up period
- % change of serum bile acids (sBA) from baseline and throughout the follow-up period

PPD/
CCI

11.7.4 Adjustment for Multiple Hypotheses Testing

Only the primary efficacy criterion will be tested confirmatorily, thus no adjustment for multiple testing is required.

11.7.5 Subgroup Analysis

No subgroup analysis is planned for this study.

11.7.6 Analyses Strategy for Pooling Trial Centers

All trial centers will be pooled for statistical summary.

11.8 Interim Analyses and Data Monitoring

No interim analyses have been planned for this study.

11.9 Statistical Analysis of Safety Endpoints

11.9.1 Safety Variables and Descriptive Summaries

Safety variables include incidence of AEs, results of ECG recordings, laboratory test results (chemistry, hematology, urinalysis and other tests specified in section 9.1.4), and physical examination findings.

Safety variables will be summarized descriptively based on the safety analysis population. No formal statistical testing will be performed for the safety analyses.

Adverse Events (AEs) will be recorded from signing the informed consent through the end of study or early termination. All AEs will be coded using the latest version of the Medical Dictionary for Regulatory Activities (MedDRA). A treatment-emergent AE (TEAE) is defined as any AE that emerges on or after first dosing of study drug or worsens relative to the pretreatment state. Various TEAEs will be summarized by MedDRA system organ class, prefer term and treatment.

Summary statistics of clinical laboratory test values at all applicable study visit and change from baseline to each post-baseline study visit will be calculated by treatment.

Vital sign results at each time point and change from baseline to each post-baseline study visit will be summarized by treatment.

ECG results at each study visit and change of these parameters from baseline to each post-baseline study visit will be summarized by treatment.

PE results will be displayed in by-patient listings.

11.10 Changes and Deviations to the Protocol and Statistical Analysis Plan

[figure not shown]
Any deviations from the planned analyses methods and the rationale for such deviations will be carefully documented in the SAP and as a protocol amendment, if applicable. The amended SAP will be submitted to the FDA. If amended, the protocol will be submitted to the IRB and to the FDA.

12.0 ACCESS TO SOURCE DATA/DOCUMENTATION

The investigative site will permit trial-related monitoring, audits, IRB/IEC review and regulatory inspections by providing direct access to source data/documentation (e.g. medical records, original laboratory records and original informed consent forms). The Investigator should immediately notify DURECT of any Health Authority inspection. Essential documents must be maintained at the investigative site throughout the trial.

12.1 Confidentiality

PPD/CCI

12.2 Data Identification

Safety laboratory results from the central safety laboratory will be considered source data. All other data will be recorded on a source document prior to being entered into the eCRF.

13.0 QUALITY CONTROL AND QUALITY ASSURANCE

13.1 Monitoring

DURECT or DURECT's designee will monitor the trial for regulatory and protocol adherence at all stages of trial conduct from inception to completion in accordance with ICH-GCP. This monitoring will be in the form of site visits and other communication and will include review of original source documents and eCRFs. DURECT's monitor or designee will notify the Investigator prior to conducting any site visit. These visits will include monitoring to assess facilities, required certifications, IRB/IEC records, equipment, patient recruiting ads, record-keeping, protocol adherence, data verification and transmission, adverse event reporting, and other factors. Final quality assurance visits by the Sponsor should be expected, and possibly by the FDA.

The completed eCRFs will be reviewed against source documents by the monitor at each monitoring visit. If any data, signatures, or forms are missing or discrepant, the Investigator will be informed and appropriate written corrections will be made in a timely manner.

13.2 Protocol Deviations

All departures from the protocol will be referred to as protocol deviations and not protocol violations (ICH E3R1 Guidance, June 2012).

Definitions

- A protocol violation is “a serious non-compliance that may lead to exclusion of a subject from analyses and/or discontinuation from the trial.”
- A protocol deviation is “related to study inclusion or exclusion criteria, conduct of the trial, subject management or subject assessment.”

An important protocol deviation is “a subset of protocol deviations that might significantly affect the completeness, accuracy, and/or reliability of the study data or that might significantly affect a subject's rights, safety, or well-being”

The Investigator should not deviate from the protocol. Except for changes intended to eliminate any immediate hazard to subjects, the trial should be conducted as described in the

approved protocol. In medical emergencies, the Investigator will use medical judgment and will remove the trial participant from immediate hazard followed by notification to DURECT and the IRB/IEC regarding the type of emergency and the course of action taken. All protocol deviations will be documented by the investigative site or monitor on the designated log.

13.3 Case Report Forms

Electronic case report forms will be used for this trial. Data entry will occur at the investigative site and will be performed by trained and qualified site personnel. The Investigator will ensure all the eCRFs are completed after each patient visit in a timely manner. Specific instructions are provided in the eCRF completion guidelines.

13.4 Coding

[figure not shown]
[figure not shown]
MedDRA will be used to code adverse events. WHO-Drug will be used to code concomitant medications.

13.5 Data Safety Monitoring Committee

A Data Safety Monitoring Committee has not been planned for this open-label trial. Periodic reviews of safety data will be performed by the Sponsor's medical monitor.

13.6 Safety Assessment Committee

In accordance with the Guidance for Industry, Safety Assessment for IND Safety Reporting, DURECT implemented a Safety Assessment Committee (SAC) to closely monitor all safety parameters ^{PPD/CCI}

14.0 ETHICAL CONSIDERATIONS

This trial will be conducted according to US and international standards of Good Clinical Practice (FDA regulations 21 CFR 312 for IND studies and ICH guidance E6) for all studies.

All subjects for this trial will be provided a consent form describing this trial and providing sufficient information for subjects to make an informed decision about their participation in this trial. This consent form will be submitted with the protocol for review and approval by the IRB. The formal consent of a subject, using the IRB-approved consent form, will be obtained before that subject is submitted to any trial procedure. This consent form must be signed by the subject or legally acceptable surrogate, and the investigator-designated research professional obtaining the consent. Each subject will be given a copy of the signed consent form.

14.1 Institutional Review Board / Ethics Committee

The protocol, consent form, advertisements and any other information for subjects will be reviewed and approved by DURECT Corporation (or DURECT's designee) and by the Institutional Review Board (IRB/Independent Ethics Committee (IEC) of the participating investigative site prior to the start of the trial at that site in accordance with the International Conference on Harmonization (ICH) and institutional IRB/IEC policies. All protocol amendments and changes to the consent form occurring during the trial must also be IRB/IEC approved.

14.2 Regulatory Compliance

The trial will be conducted in accordance with the principles of Good Clinical Practice (GCP) set forth in the International Conference on Harmonization (ICH) Good Clinical Practice, the US Code of Federal Regulations (CFR Title 21), the Health Insurance Portability and Accountability Act of 1996 (HIPAA) and any local requirements.

14.3 Regulatory Status

DUR-928 is under development and has not been approved for commercial use.

14.4 Patient Information and Informed Consent

Prior to participation in the trial, the Investigator or designee will obtain written consent from each patient using the IRB/IEC-approved informed consent form that explains the nature, purpose, possible risks and benefits of the trial, and the duration of an individual's participation. The basic elements of the informed consent as specified by the FDA (21 CFR §50.25), and HIPAA will be followed.

Before consenting, the patient must be left with ample time to consider and to pose questions. The Investigator and/or the designated investigative site personnel who conduct the informed consent discussion must also sign and date the consent form. Each patient will be given a copy of the signed consent form. The original, signed consent forms will be maintained at the investigative site.

